7.3. Intervention – Procedural (if applicable)

Description:

The training manual for this intervention is based on the Appetite Awareness Training Workbook by Linda Craighead.

Training on Procedural Intervention:

MSW-trained social work clinicians will be responsible for conducting both interventions, and will have weekly supervision with the PI ([name]). Due to their training in the social determinants of health and in providing behavioral health interventions, social workers with graduate training are well-equipped to apply a person-in-environment perspective, and treat the biopsychosocial factors that influence the health and eating behaviors of study participants. Moreover, using social workers may reduce burden in a busy, primary care setting, and increase treatment access and uptake.

7.4. Concomitant Therapy (if applicable)

[Describe what is prohibited, what is recommended and/or allowed, and what information about this topic will be collected as part of the study.]

N/A

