5.4. Outcome Measures

Primary Outcome(s):

Table 2: Feasibility Measures (Aim #1) ³⁸	
Question of Interest	Feasibility Measures
Can we recruit our target population?	# of screened and eligible participants, and proportion of eligible screens who enroll
Will participants do what they are asked to do?	Adherence to study protocol (e.g. session attendance, homework completion)
Are the assessments too burdensome?	Proportion of planned assessments completed; duration of assessment visits
Will participants stay in the study?	% of study retention and reasons for dropouts
Is AAT + NUTR acceptable to study participants?	Semi-structured telephone interviews (n=15-20) will be conducted to receive feedback on intervention and suggestions for improvement.

Secondary Outcome(s): Linear mixed effects modeling will be used to examine the association between treatment group assignment (AAT + BWL or wait-list control group coded as a (0,1)-indicator) and binge eating, eating self-efficacy, depressive symptoms, weight, blood pressure, and waist circumference scores at 2 and 6 months.

6. Study Participants

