7.7. Withdrawal / Discontinuation of Enrolled Participants

Participants may be withdrawn if participant develops a condition that is an exclusion criterion (e.g. participants who become pregnant will be asked to withdraw from the study).

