8.4. Study Visits (Numbered as V1, V2, etc., Day X ± Y)

Participants will attend 8 weekly AAT sessions and then transition to eight, weekly NUTR sessions. All sessions will be 60-90 minutes.

V1: Data on AAT group and control group collected at baseline, before randomization (T1)

V2: Data on AAT group and control group collected at end of month 4, after completion of intervention program (T2)

V3: Data on AAT group and control group collected data end of month 6, posttreatment follow-up (T3)

Data collected includes height, weight, blood pressure, and waist circumference.

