8.8. Premature Discontinuation

[If a subject withdraws or the investigator discontinues subject participation, specify evaluations that should be performed and data that should be collected. Indicate if you plan to collect medical record data for the duration of the study for follow-up purposes, even if the study intervention is discontinued.]

<If a participant withdraws or study participation is discontinued by the principal investigator, participants will be asked to complete the Eating Disorder Examination-Questionnaire Survey.

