At 4 and 6 months, compare changes in (a) binge eating, eating self-efficacy, and depressive symptoms and (b) weight for participants in the AAT vs. control group. Linear mixed effects modeling will be used to examine the association between treatment group assignment (AAT + BWL or wait-list control group coded as a (0,1)-indicator) and binge eating, eating self-efficacy, depressive symptoms, weight, blood pressure, and waist circumference scores at 2 and 6 months. Baseline scores will be used as covariates in these analyses with interactions between treatment group assignments with baseline values of outcome scores. Standardized mean differences (e.g., Cohen's d with bias adjustment) will also be calculated as an effect size measure with 95% CI. Standardized residuals will be examined to assure no assumptions are violated.

Plans for Aim 3: N/A

Plans for Aim 4: N/A

10.4.Planned Interim Analyses (If Applicable)

N/A

10.5.Plans for Coping with Withdrawals and Loss-To-Follow-Up

Enrolled participants who discontinue/are withdrawn will not be replaced. The initial target number of enrolled participants is large enough to cope with loss of participants' data due to discontinuation, withdrawal, or insufficiently complete data (missing values).

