11.2. Assessment of Safety

To minimize emotional distress, if participants cite this concern, they will be provided the option to a) pause

and regroup; and/or b) finish the survey at a later time. If the previous is not sufficient, and participants report experiencing significant distress, participants will be provided the number to Hopeline (<https://www.hopeline-nc.org>; [contact]), a North Carolina crisis line and to the local emergency room.

Participants who experience significant distress will also be asked permission to provide their contact information to the PI ([name]). [name], who is a licensed clinical social worker, will contact those

participants on the next day. [name] will also be updated immediately on all participants who experience

significant distress.

Depression – Beck Depression Inventory

Using the total score (from all added scores on the BDI), the following interpretation applies:

Total Score	Range of Depression
0 – 13	Minimal
14 – 19	Mild
20 – 28	Moderate
29 – 63	Severe

Potential participants who on initial assessment (or is there a screening assessment) have a BDI-II score of 29 or greater (“severe” depression) are excluded from the study (please see below).

If a participant’s total score is 20 or greater, this will be reported to the Principal Investigator (PI) or Project Director (PD) who will discuss their results, inquire about current status and

treatment, will **provide information on community resources for the treatment of depression, and document the conversation and actions taken.**

For question #9 “Suicidal Thoughts or Wishes”: If a participant chooses response option 1, 2 or 3, this will be reported to the PI or PD who will discuss the results, inquire about current status and treatment and document the conversation and actions taken (providing a detailed note of the discussion that will be maintained using the participant’s ID number). The participant will also be referred to their PCP, given a list of mental health providers in the community, and urged to seek treatment if they are not already receiving treatment.

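### Section 7.7 permits withdrawing a randomised woman who starts an excluded outside treatment, and most of her later outcomes would then not be requested

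*Combined protocol and SAP*

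**What the plan says.** - **Withdrawal rule (7.7).** "Participants may be withdrawn if participant develops a condition that is an exclusion criterion". The only example given is pregnancy.
- **Exclusion criteria.** Section 6.2 excludes women currently treated for disordered eating or in substance-use treatment. The synopsis also excludes women in a weight-loss programme; 6.2 does not repeat this.
- **Data after withdrawal (8.8).** On withdrawal or discontinuation, "participants will be asked to complete the Eating Disorder Examination-Questionnaire Survey". No other measure is requested, and nothing is said about the month 4 and month 6 visits.
- **Outcomes modelled (10.3, plans for Aim 2).** The mixed models cover "binge eating, eating self-efficacy, depressive symptoms, weight, blood pressure, and waist circumference scores", with baseline values as covariates.
- **Handling of losses.** Withdrawn women are not replaced (10.5). Reasons for drop-out are to be documented (10.1).
- **Outside care (7.4).** The template prompt, "Describe what is prohibited, what is recommended and/or allowed, and what information about this topic will be collected as part of the study", is answered N/A. The schedules in 5.3 and 8.1 and the visit descriptions in 8.4, 8.6 and 8.7 contain no item on treatment received elsewhere.
- **The one exception (11.2).** If a woman endorses BDI item 9, the PI or project director will "discuss the results, inquire about current status and treatment and document the conversation and actions taken". A BDI total of 20 or more leads to a similar documented enquiry. The BDI is scheduled for both arms at baseline, 4 and 6 months.
- **Comparator (5.1).** Controls are offered a shortened AAT once six months have passed.

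**The concern.** An eligibility criterion decides who enters a trial. Section 7.7 lets the same criterion decide who stays in follow-up. For pregnancy there is an obvious reason, since weight is an outcome. For outside treatment there is not. A woman who seeks treatment for binge eating during the six months probably does so because of how her eating is going, so her outcomes are unlikely to resemble those of women who do not. Withdrawing her makes her later data missing through a staff decision, for a reason tied to the outcome, when she might willingly have attended the visits. That weakens the as-randomised comparison in Aim 2.

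The second matter is descriptive. Outside care used during a six-month wait is part of what the wait-list arm received, and is not in itself a bias. Without a routine record, the report cannot say what that comparator was.

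**Working it through.** **1. Can 7.7 reach outside treatment?** Set side by side, 7.7 refers to a condition that is an exclusion criterion, and 6.2 lists current eating-disorder treatment and substance-use treatment as such criteria. The synopsis adds a weight-loss programme. Nothing in 7.7 limits the rule to medical conditions. The rule can therefore be applied to a woman who starts such treatment, but nothing shows that it would be. Treatment for depression is not among the criteria; 11.2 excludes on a severe BDI score at initial assessment, not on treatment.

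**2. What would be lost?** Of the outcomes modelled in 10.3:

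| Outcome | Requested after withdrawal (8.8)? |
|---|---|
| Binge eating | In part: EDE-Q yes, EDE interview no |
| Eating self-efficacy | No |
| Depressive symptoms | No |
| Weight | No |
| Blood pressure | No |
| Waist circumference | No |

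That is 6 − 1 = 5 of 6 not requested. Aim 2 as worded in 3.2 lists binge eating, depressive symptoms, diet and weight; on that list it is 4 − 1 = 3 of 4. Values collected before withdrawal remain, so a woman withdrawn after month 4 loses only her month 6 values.

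**3. What would the model do?** Baseline is a covariate, so the responses are the post-baseline values. For these five outcomes, a woman withdrawn before month 4 contributes no response unless her values are imputed. Imputation is only a possible remedy in 10.2, and it would borrow from women who were not withdrawn.

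**4. How large is one withdrawal?** The documents give totals of 60 and 48, hence 30 or 24 per arm. 1/30 = 3.3% and 1/24 = 4.2% of an arm.

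**5. Is it a power problem?** Section 10.6 states power of 0.80 for d = 0.74 with 60 women. A two-sample t-test with 30 per arm gives 0.805 (two-sided 5% assumed, as the plan states no alpha), so the figure reproduces. If three women were lost from one arm (illustrative), 30 versus 27 gives 0.782. The cost in power is small; the issue is which women are missing.

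**6. What would a record of outside care show?** With illustrative counts, 5/24 has an exact 95% interval of 7.1% to 42.2%, and 5/30 of 5.6% to 34.7%. The difference 5/24 − 2/24 is 12.5 points (Newcombe 95% interval −8.5 to 33.0). Such a table describes the arms; it cannot separate them.

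**The case against.** The strongest reply is that the withdrawal route is an inference. Section 7.7 is permissive, speaks of a condition, and names only pregnancy. Reasons for drop-out are documented, the EDE-Q is still requested, and the thin data request in 8.8 affects every withdrawal, whatever its cause. The study puts feasibility ahead of efficacy (10.6). Section 7.4 is headed as optional, and the template allows N/A. All of this is fair and keeps the point minor. It does not remove it: the rule permits the withdrawal, nothing rules it out, and documenting a reason does not recover the missing outcomes.

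Four stronger readings are tempting, and the documents do not support them.

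- **Nobody is ever asked about outside treatment.** Section 11.2 requires a documented enquiry for women flagged by the BDI, in both arms. It covers a subset, is prompted by depression safety, and is not set up as analysis data.
- **Any outside care could end participation.** Depression treatment is not an exclusion criterion, and 11.2 urges some women to seek it.
- **Withdrawals would be detected more often in the intervention arm.** A reader might infer this from "Participants will attend 8 weekly AAT sessions and then transition to eight, weekly NUTR sessions" and from clinicians who "will have weekly supervision with the PI". No section says that session clinicians ask about outside care or pass it on. Controls also have scheduled contacts, including telephone dietary recalls at month 6, and might equally seek more care because they are waiting. The direction is undetermined.
- **The result is biased by some amount.** The documents give no rate of outside care, of such withdrawals, or of their effect.

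**Conclusion.** The point holds as a minor one. Sections 7.7, 6.2 and 8.8 together allow avoidable loss of outcomes after randomisation, for a reason related to outcome. Per woman, the loss is the later values of five of the six outcomes in 10.3, or 3.3% to 4.2% of an arm. If such a withdrawal counts as attrition, arm retention falls by the same number of points, and Table 2 in 5.4 makes the percentage "of study retention and reasons for dropouts" a feasibility measure. The conclusion assumes that 7.7 would be applied to started treatment, which its wording permits but does not require. How often this would happen, whether it would differ by arm, and which way it would move an estimate cannot be determined. The lack of a routine record of outside care is a secondary gap in description and changes no planned result.

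**What to change.** **Main change, in 7.7.** State that taking up outside treatment after randomisation does not by itself lead to withdrawal, and that these women stay in the month 4 and month 6 assessments and in the Aim 2 analysis as randomised. Pregnancy can remain a reason for withdrawal. This takes a sentence or two and needs no change to the sample size or model. The price is one of interpretation: Aim 2 then compares the intervention with wait-list, each with whatever outside care was used, and the report should say so.

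**Secondary and optional, in 7.4.** Replace N/A with a short item for both arms at months 4 and 6 on psychotherapy or eating-disorder treatment, psychiatric or weight-loss medication, and weight programmes, with start dates. Tabulate counts by arm with intervals and no test. The cost is one table and a few minutes per visit (2 to 3 assumed), in a study that itself asks whether its assessments are too burdensome.

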7.5. Rescue Medications and Procedures (if applicable)

[Describe rescue procedures or medications that are permissible or required for adverse events.]

N/A

7.6. Compliance Checks

[Discuss measures and procedures to assess participant compliance.]

N/A

7.7. Withdrawal / Discontinuation of Enrolled Participants

Participants may be withdrawn if participant develops a condition that is an exclusion criterion (e.g. participants who become pregnant will be asked to withdraw from the study).

7.8. Voluntary Withdrawal (Drop-Out) of Enrolled Participants

Participants may voluntarily withdraw participation at any time, for any reason, with no penalty or loss of rights. If a participant withdraws prior to the completion of a particular assessment, the participant will only have access to incentives based on what assessments were previously completed.

8. Study Procedures and Schedule

[Information presented in this section should be consistent with the Synopsis (MPD Section 1) and the Table of Events (example below)]

8.1. Table of Events

Measure	Description	Assessment Schedule		
		Baseline	4 months	6 months
Eating Disorder Examination – Overeating Section (EDE) ³⁵	A semi-structured interview to assess symptoms and DSM-V diagnoses for Bulimia Nervosa, Anorexia Nervosa, and BED.	X	X	X
Modified Sociodemographic Questionnaire	A questionnaire to collect age, marital status, education, neighborhood residence, employment status, household size, religious background, and income	X		
Height /Weight	Will be measured on a digital scale and a portable stadiometer.	X	X	X
Eating Disorder Examination-Questionnaire (EDE-Q) ³⁶	A 41-item scale to assess disordered eating behaviors and attitudes.	X	X	X
Dietary Intake (e.g., overall energy intake, fat, fruit and vegetable intake)	Two-24-hr dietary recall interviews (telephone-based) will be conducted on randomly selected days during a 2-week period.	X		X
Beck Depression Inventory ³⁷	A 21-item instrument used for measuring attitudes and symptoms of depression.	X	X	X

[In the following sections 7.2 – 7.8, fully describe:

- All contact with subjects (study visits, telephone/electronic contact)
- Permissible time windows for study procedures, lab tests, etc. While a treatment visit may have a small window (such as ± 1 day),

a 6-month follow-up call may have larger window (such as ± 1 week)

- Clearly distinguish activities and procedures that participants will complete in the course of clinical care from those that participants will complete solely for research purposes]

Study Activities	Year 01				Year 02			
	Q1	Q2	Q3	Q4	Q1	Q2	Q3	Q4
Aim 1: Feasibility Study								
Start-up								
Recruitment								
Conduct of feasibility study								
Data Analysis								
Presentations and publications								
Aim 2: Acceptability Interviews								
Semi-structured interviews and analysis								
Presentations and publications								
Prepare and submit R-series grant								

8.2. Pre-Screening / Screening (Day -X to Day Y)

During recruitment, participants will not be directly contacted identified from privately held sources without the participant's permission. Methods that are the "least intrusive" will be used, and participants will be encouraged to contact the research team if they are interested in receiving more information about the study. Participants will self-refer to the study, and provided the link to participate in the survey. Participants will be contacted by email or telephone to after determining preliminary eligibility via a Qualtrics web survey. Recruitment will be managed by study investigators and research assistants. Potential participants will respond to notices by calling number on flyer or filling out the screening link, and will be screened to determine eligibility. If an individual is eligible, she will be given a date and time to meet with a research team member.

8.3. Enrollment / Baseline (Day 0)

If participants are eligible for the study, the applicant will be given a date and time to meet with the PI and will be provided an email link to access the self-report measures associated with this study. At appointment, participants will provide signed informed consent, finish self-report measures, and be evaluated in person to determine the presence of at least one weekly binge eating episode using the overeating section of the Eating Disorder Examination. Participants will also have their height, weight, blood pressure, and waist circumference measured at this time. Baseline appointment will take place in a private room at the UNC Department of Family Medicine. If all inclusion criteria are met, participants will be randomly assigned to one of the two treatment conditions.

8.4. Study Visits (Numbered as V1, V2, etc., Day X ± Y)

Participants will attend 8 weekly AAT sessions and then transition to eight, weekly NUTR sessions. All sessions will be 60-90 minutes.

V1: Data on AAT group and control group collected at baseline, before randomization (T1)

V2: Data on AAT group and control group collected at end of month 4, after completion of intervention program (T2)

V3: Data on AAT group and control group collected data end of month 6, posttreatment follow-up (T3)

Data collected includes height, weight, blood pressure, and waist circumference.

8.5. Phone Contact (Day Day X ± Y)

[Describe information/data to be collected, e.g., activities of daily living, symptom rating.]

<Insert text>

8.6. Final Visit (Day Day X ± Y)

[List all interventions/evaluations/procedures in the sequence they will occur, e.g., record adverse events as reported by subject or observed by investigator, record subject's compliance with intervention, provide final instruction to subject.]

<Insert text>

Data collected at end of month 4, after the completion of intervention program, includes: height, weight, blood pressure, and waist circumference. Participants will also be asked to complete the Eating Disorder Examination, Eating Disorder Examination-Questionnaire, Weight Efficacy Lifestyle Questionnaire, and the Beck Depression Inventory.

8.7. Follow-Up Contact (Day Day X ± Y)

[Describe information/data to be collected, e.g., adverse events, disease progression/recurrence.]

<Insert text>

Data collected at end of month 6, posttreatment follow up, includes: height, weight, blood pressure, and waist circumference. Participants will also be asked to complete the Eating Disorder Examination, Eating Disorder Examination-Questionnaire, Weight Efficacy Lifestyle Questionnaire, and the Beck Depression Inventory.

8.8. Premature Discontinuation

[If a subject withdraws or the investigator discontinues subject participation, specify evaluations that should be performed and data that should be collected. Indicate if you plan to collect medical record data for the duration of the study for follow-up purposes, even if the study intervention is discontinued.]

<If a participant withdraws or study participation is discontinued by the principal investigator, participants will be asked to complete the Eating Disorder Examination-Questionnaire Survey.

8.9. Collection and Management of Tissue Specimens

Sample Preparation: [As applicable, describe measures to prevent sample loss and degradation, cooling and freezing procedures, sample labeling, etc.]

Record Keeping and Monitoring: [As applicable, describe procedures for maintaining sample accountability and traceability and for ensuring regulatory compliance.]

Sample Storage and Security: [As applicable, describe the location, facility, and storage method/equipment; sample chain of custody; the remote monitoring and maintenance procedures; data security system, encryption, and access restrictions for study personnel.]

9. Study Measurements and Evaluations

9.1. Outcome Measures for Evaluation of Feasibility / Tolerability

To assess the feasibility of recruiting adult, AA women to the proposed study, the percent of eligible women who were enrolled and retained in the study will be examined and reasons for nonparticipation and attrition will be documented. Feasibility will also be determined by calculation of point and interval estimates (95% confidence intervals using sample size methods) of the feasibility parameters (proportion/percentages in terms of eligibility, participation, retention; means/medians for attendance at intervention sessions) and bivariate frequency distributions.

Question of Interest	Feasibility Measures
Can we recruit our target population?	# of screened and eligible participants, and proportion of eligible screens who enroll
Will participants do what they are asked to do?	Adherence to study protocol (e.g. session attendance, homework completion)
Are the assessments too burdensome?	Proportion of planned assessments completed; duration of assessment visits
Will participants stay in the study?	% of study retention and reasons for dropouts
Is AAT + NUTR acceptable to study participants?	Semi-structured telephone interviews (n=15-20) will be conducted to receive feedback on intervention and suggestions for improvement.

